6.1 Primary Safety Endpoint

The primary safety endpoint for this study is the Composite Safety Endpoint (CSE) defined as the incidence of the following early-onset and late-onset serious adverse events (SAEs) which are device- or procedure-related, as adjudicated by the CEDMC and defined below in **Table 4. Composite Safety Endpoint Definitions**.

Early onset (within 30 days of an Index or Remap Procedure)

- Death
- Myocardial infarction (MI)
- Persistent diaphragmatic paralysis
- Stroke or transient ischemic attack (TIA)
- Peripheral or organ thromboembolism
- Pericarditis
- Cardiac tamponade / perforation
- Vascular access complications requiring intervention
- Heart block

Late onset (any time during follow-up through 12 months)

- Pulmonary vein (PV) stenosis (> 70% diameter reduction from baseline)
- Atrio-esophageal fistula

Table 4. Composite Safety Endpoint Definitions

Adverse Event	Description/Criteria
Death	Death
Myocardial infarction (MI)	Myocardial infarction will be demonstrated by any one of the following: 1) detection of ECG changes indicative of new ischemia (new ST-T wave changes or new LBB) that persist for more than 1 hour. 2) development of new pathological Q waves on an ECG 3) imaging evidence of new loss of viable myocardium or new regional wall motion abnormality
Persistent diaphragmatic paralysis	Diaphragmatic paralysis: Change from baseline diaphragmatic function as demonstrated radiographically by elevation of the diaphragm above the normal range but not due to a pulmonary process such as atelectasis. Permanent: not resolved by completion of study follow-up
Stroke or transient ischemic attack (TIA)	Stroke is an acute symptomatic episode of neurological dysfunction attributed to a vascular cause (ischemia or hemorrhage) in which symptoms last more than 24 hours, or if symptoms last less than 24 hours, a brain imaging study demonstrates infarction. Transient ischemic attack is a new focal neurological deficit with rapid symptom resolution always within 24 hours.

Adverse Event	Description/Criteria
Peripheral or organ thromboembolism	Formation in a blood vessel of a clot (thrombus) that results from the breaking loose of all or part of an existing thrombus, which is then carried by the blood to lodge in/occlude a more distal vascular site.

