ELSE New or Prolonged Hospitalization, excl. AF/AFL ='No'

CONFIDENTIEL / CONFIDENTIAL

Toute reproduction ou distribution, totale ou partielle, de ce document, sans autorisation préalable de ICON PLC est interdite.
Reproduction and distribution of this document, in whole or in part, is strictly forbidden without prior authorization from ICON PLC.

	STATISTICAL ANALYSIS PLAN	FARAPULSE PersAFOne SAP V1.0 PERSAFONE Page 28 /49
---	----------------------------------	--

- Derived criteria “Vascular Access Complication” will be defined as follows:
IF (30≤ (EVENT DATE-PROCEDURE DATE IN PROCEDURAL DATA FORM (PR)) **OR** (30≤ (EVENT DATE-REMAPPING DATE IN FOLLOW-UP 3D ELECTROANATOMICAL MAPPING FORM (RM)) **AND** PRIMARY SAFETY ENDPOINT EVENT CRITERIA=’ Vascular Access Complication’ **THEN** Vascular Access Complication =’Yes’
ELSE Vascular Access Complication =’No’
- Derived criteria “Total Early and Late Onset Composite Safety Endpoint” will be defined as follows:
IF Death=Yes **OR** Myocardial infarction =Yes **OR** PV Stenosis =Yes **OR** Diaphragmatic Paralysis =Yes **OR** AE fistula =Yes **OR** TIA =Yes **OR** CVA=Yes **OR** Major pericarditis =Yes **OR** Tamponade/Perforation =Yes **OR** Pneumothorax =Yes **OR** Heart Block =Yes **OR** Pulmonary Edema =Yes **OR** New or Prolonged Hospitalization, excl. AF/AFL =Yes **OR** Vascular Access Complication =Yes **THEN** Total Early and Late Onset Composite Safety Endpoint =’Yes’
ELSE Total Early and Late Onset Composite Safety Endpoint =’No’
- Derived criteria “Total Early Onset Composite Safety Endpoint” will be defined as follows:
IF Death=Yes **OR** Myocardial infarction =Yes **OR** Diaphragmatic Paralysis =Yes **OR** TIA =Yes **OR** CVA=Yes **OR** Major pericarditis =Yes **OR** Tamponade/Perforation =Yes **OR** Heart Block =Yes **OR** New or Prolonged Hospitalization, excl. AF/AFL =Yes **OR** Vascular Access Complication =Yes **THEN** Total Early Onset Composite Safety Endpoint=’Yes’
ELSE Total Early Onset Composite Safety Endpoint=’No’
- Derived criteria “Total Late (any time during follow-up through 12 months)” will be defined as follows:
IF PV Stenosis =Yes **OR** AE fistula =Yes **THEN** Total Late (any time during follow-up through 12 months) =’Yes’
ELSE Total Late (any time during follow-up through 12 months) =’No’.

Secondary Safety endpoint

- Derived criteria “Death 7 days” will be defined as follows:

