IF (7≤ (EVENT DATE-PROCEDURE DATE IN PROCEDURAL DATA FORM (PR)) **OR** (7≤ (EVENT DATE-REMAPPING DATE IN FOLLOW-UP 3D ELECTROANATOMICAL MAPPING FORM (RM)) **AND** PRIMARY SAFETY ENDPOINT EVENT CRITERIA=' Tamponade/Perforation' **THEN** Tamponade/Perforation ='Yes'.
ELSE Tamponade/Perforation = 'No'.

- Derived criteria "Pneumothorax 7 days" will be defined as follows:

IF (7≤ (EVENT DATE-PROCEDURE DATE IN PROCEDURAL DATA FORM (PR)) **OR** (7≤ (EVENT DATE-REMAPPING DATE IN FOLLOW-UP 3D ELECTROANATOMICAL MAPPING FORM (RM)) **AND** PRIMARY SAFETY ENDPOINT EVENT CRITERIA=' Pneumothorax' **THEN** Pneumothorax ='Yes'. **ELSE** Pneumothorax = 'No'.

- Derived criteria "Heart Block 7 days" will be defined as follows:

IF (7≤ (EVENT DATE-PROCEDURE DATE IN PROCEDURAL DATA FORM (PR)) **OR** (7≤ (EVENT DATE-REMAPPING DATE IN FOLLOW-UP 3D ELECTROANATOMICAL MAPPING FORM (RM)) **AND** PRIMARY SAFETY ENDPOINT EVENT CRITERIA=' Heart Block' **THEN** Heart Block = 'Yes'.
ELSE Heart Block = 'No'.

- Derived criteria "Pulmonary Edema 7 days" will be defined as follows:

CONFIDENTIEL / CONFIDENTIAL

Toute reproduction ou distribution, totale ou partielle, de ce document, sans autorisation préalable de ICON PLC est interdite.
Reproduction and distribution of this document, in whole or in part, is strictly forbidden without prior authorization from ICON PLC.

	STATISTICAL ANALYSIS PLAN	FARAPULSE PersAFOne SAP V1.0 PERSAFONE Page 30 /49
---	----------------------------------	--

IF (7≤ (EVENT DATE-PROCEDURE DATE IN PROCEDURAL DATA FORM (PR)) **OR** (7≤ (EVENT DATE-REMAPPING DATE IN FOLLOW-UP 3D ELECTROANATOMICAL MAPPING FORM (RM)) **AND** PRIMARY SAFETY ENDPOINT EVENT CRITERIA=' Pulmonary Edema' **THEN** Pulmonary Edema = 'Yes'.
ELSE Pulmonary Edema = 'No'.

- Derived criteria "New or Prolonged Hospitalization, excl. AF/AFL 7 days" will be defined as follows:
IF (7≤ (EVENT DATE-PROCEDURE DATE IN PROCEDURAL DATA FORM (PR)) **OR** (7≤ (EVENT DATE-REMAPPING DATE IN FOLLOW-UP 3D ELECTROANATOMICAL MAPPING FORM (RM)) **AND** PRIMARY SAFETY ENDPOINT EVENT CRITERIA=' New or Prolonged Hospitalization, excl. AF/AFL' **THEN** New or Prolonged Hospitalization, excl. AF/AFL = 'Yes'.
ELSE New or Prolonged Hospitalization, excl. AF/AFL = 'No'.
- Derived criteria "Vascular Access Complication 7 days" will be defined as follows:

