IF (7≤ (EVENT DATE-PROCEDURE DATE IN PROCEDURAL DATA FORM (PR)) **OR** (7≤ (EVENT DATE-REMAPPING DATE IN FOLLOW-UP 3D ELECTROANATOMICAL MAPPING FORM (RM)) **AND** PRIMARY SAFETY ENDPOINT EVENT CRITERIA=' Vascular Access Complication' **THEN** Vascular Access Complication = 'Yes'.
ELSE Vascular Access Complication = 'No'.
- Derived criteria "Total Early Onset Composite Safety Endpoint assessed at 7 days" will be defined as follows:
IF Death 7 days='Yes' **OR** Myocardial infarction 7 days='Yes' **OR** Diaphragmatic Paralysis 7 days='Yes' **OR** TIA 7 days='Yes' **OR** CVA 7 days='Yes' **OR** Major pericarditis 7 days='Yes' **OR** Tamponade/Perforation 7 days='Yes' **OR** Heart Block 7 days='Yes' **OR** New or Prolonged Hospitalization, excl. AF/AFL 7 days='Yes' **OR** Vascular Access Complication 7 days='Yes' **THEN** Total Early Onset Composite Safety Endpoint assessed at 7 days = 'Yes'.
ELSE Total Early Onset Composite Safety Endpoint assessed at 7 days = 'No'.
- Derived criteria "Device-Related Serious Adverse Events (SAEs)" will be defined as follows:
IF CEC seriousness ="Serious" **AND** CEC relationship to study Device in (Causal relationship, Probably related, Possibly related, Unlikely to be related) in adverse event adjudication form **THEN** Device-Related Serious Adverse Events (SAEs)='Yes'; **ELSE** Device-Related Serious Adverse Events (SAEs)='No'
- Derived criteria "Procedure-Related Serious Adverse Events (SAEs)" will be defined as follows:
IF CEC relationship to study procedure in (Causal relationship, Probably related, Possibly related, Unlikely to be related) **AND** CEC seriousness ='Serious' **THEN** Procedure-Related Serious Adverse Events (SAEs)='Yes'
ELSE IF CEC relationship to study procedure ='Not related' **AND** CEC seriousness =" Serious" **THEN** Procedure-Related Serious Adverse Events (SAEs)='No'
- Derived criteria "Cardioversion" will be defined as follows:
IF Arrhythmia-Treatment DC Cardioversion is ticked in **Arrhythmia episodes form** **THEN** Cardioversion ='Yes';
ELSE Cardioversion ='No'

CONFIDENTIEL / CONFIDENTIAL

Toute reproduction ou distribution, totale ou partielle, de ce document, sans autorisation préalable de ICON PLC est interdite.
Reproduction and distribution of this document, in whole or in part, is strictly forbidden without prior authorization from ICON PLC.

	STATISTICAL ANALYSIS PLAN	FARAPULSE PersAFOne SAP V1.0 PERSAFONE Page 31 /49
---	----------------------------------	--

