4.1.12. Table 12. Secondary Safety Endpoints

	ITT Population N = XX	
	n/N (%)	[95% CI]
Primary Safety Endpoint (Early and Late Onset Composite Safety Endpoint) assessed at 7 days	XX/XX (XX.X%)	[XX% - XX%]
Total Early (within 30 days of Index or Remap Procedure)	XX/XX (XX.X%)	[XX% - XX%]
Death	XX/XX (XX.X%)	[XX% - XX%]
Myocardial infarction (MI)	XX/XX (XX.X%)	[XX% - XX%]
Persistent diaphragmatic paralysis	XX/XX (XX.X%)	[XX% - XX%]
Stroke	XX/XX (XX.X%)	[XX% - XX%]
Transient ischemic attack (TIA)	XX/XX (XX.X%)	[XX% - XX%]
Peripheral or organ thromboembolism	XX/XX (XX.X%)	[XX% - XX%]
Pericarditis	XX/XX (XX.X%)	[XX% - XX%]
Cardiac tamponade / perforation	XX/XX (XX.X%)	[XX% - XX%]
Vascular access complications requiring intervention	XX/XX (XX.X%)	[XX% - XX%]
Heart block	XX/XX (XX.X%)	[XX% - XX%]
Total Late (any time during follow-up through 12 months)	XX/XX (XX.X%)	[XX% - XX%]

CONFIDENTIEL / CONFIDENTIAL

Toute reproduction ou distribution, totale ou partielle, de ce document, sans autorisation préalable de ICON PLC est interdite.
Reproduction and distribution of this document, in whole or in part, is strictly forbidden without prior authorization from ICON PLC.

ICON	STATISTICAL ANALYSIS PLAN	FARAPULSE PersAFOne SAP V1.0 PERSAFONE Page 43 /49
-------------	----------------------------------	--

Pulmonary vein (PV) stenosis (> 70% diameter reduction from baseline)	XX/XX (XX.X%)	[XX% - XX%]
Atrio-esophageal fistula	XX/XX (XX.X%)	[XX% - XX%]
Device-Related Serious Adverse Events (SAEs)	XX/XX (XX.X%)	[XX% - XX%]
Procedure-Related Serious Adverse Events (SAEs)	XX/XX (XX.X%)	[XX% - XX%]
Stroke	XX/XX (XX.X%)	[XX% - XX%]
Transient Ischemic Attack (TIA)	XX/XX (XX.X%)	[XX% - XX%]
Cardioversion	XX/XX (XX.X%)	[XX% - XX%]
Arrhythmia-related (AF, AFL, AT) hospitalization	XX/XX (XX.X%)	[XX% - XX%]

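### The SAP's composite safety rules do not compute the Protocol 6.1 endpoint: thromboembolism is missing, and hospitalization, pneumothorax and pulmonary edema are added

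*SAP*

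**What the plan says.** Protocol 6.1 lists nine early-onset items, counted within 30 days of an Index or Remap Procedure, and two late-onset items, counted through 12 months. One early item is "Peripheral or organ thromboembolism". SAP 2.4.8.1 repeats the list, and the shells of SAP Tables 8 and 12 print it.

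The rules in SAP 2.5 differ:

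- The overall rule and the 30-day early rule both contain "New or Prolonged Hospitalization, excl. AF/AFL =Yes".
- The overall rule also contains "Pneumothorax =Yes" and "Pulmonary Edema =Yes".
- The 7-day early rule contains "New or Prolonged Hospitalization, excl. AF/AFL 7 days".
- No thromboembolism variable is derived anywhere in SAP 2.5.
- A variable "Pulmonary Edema 7 days" and its pneumothorax counterpart are derived but feed no composite.

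Table 12's top row is "Primary Safety Endpoint (Early and Late Onset Composite Safety Endpoint) assessed at 7 days", for which SAP 2.5 has no rule. Its sub-row is still labelled "Total Early (within 30 days of Index or Remap Procedure)".

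The early windows are coded as 30 ≤ (event date − procedure date), or 7 ≤ for the 7-day versions. The late items stop at day 360.

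A secondary point concerns related SAEs. SAP 2.5 counts a serious event as device-related if the committee rates it causal, probable, possible or unlikely. Protocol 7.3.1 Note 3 limits device-related, for this protocol, to probably or definitely. Protocol 6.2 and SAP 2.4.8.2 ask for one proportion, device- or procedure-related. SAP 2.5 and Table 12 give two.

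**The concern.** A descriptive study with no hypothesis test has only the reported rate and its interval as its primary safety result. If the executable rule differs from the definition, the reported figure is not the CSE.

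The two kinds of difference act in opposite directions. A thromboembolic event is a protocol CSE component but has no variable through which to reach the total. An admission for a reason outside the protocol list could count. Pneumothorax and pulmonary edema enter the overall total but neither sub-total, so Table 8's top row could exceed what its printed parts explain. Its thromboembolism row has nothing to fill it. Table 15 and Listings 14 and 17 might reveal a discrepancy to a careful reader, but they would not correct the primary rate.

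**Working it through.** The plan states no figure to reproduce, so the check compares the lists and then sizes the effect.

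**1. Mapping assumed.** CVA = stroke; major pericarditis = pericarditis; diaphragmatic paralysis = persistent paralysis; vascular access complication = one requiring intervention. Stroke and TIA are counted separately, so the protocol list has 10 early + 2 late = 12 items.

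**2. Set comparison with Protocol 6.1.**

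| SAP 2.5 rule | Terms | Omits | Adds |
|---|---|---|---|
| Overall | 14 | thromboembolism | hospitalization, pneumothorax, pulmonary edema |
| Early, 30 days | 10 | thromboembolism | hospitalization |
| Early, 7 days | 10 | thromboembolism | hospitalization |
| Late | 2 | none | none |

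Check on counts: 12 − 1 + 3 = 14 overall; 10 − 1 + 1 = 10 for each early rule.

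**3. Internal consistency.** Overall minus (early or late) = {pneumothorax, pulmonary edema}. The total is therefore not the union of its two sub-totals.

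**4. Effect of one subject.** SAP 2.1.4 uses the Agresti-Coull interval at 0% and, where the asymptotic assumptions fail, the exact interval otherwise. Agresti-Coull with z = 1.96: ñ = n + z²; p̃ = (x + z²/2)/ñ; upper limit = p̃ + z√[p̃(1 − p̃)/ñ].

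- 0/40: ñ = 43.84, p̃ = 0.0438, upper limit = 0.0438 + 0.0606 = 10.4%. For 1/40 = 2.5%, the exact interval is 0.1–13.2%.
- 0/25 (the N printed in the shells of SAP Tables 5 and 19): ñ = 28.84, p̃ = 0.0666, upper limit = 0.0666 + 0.0910 = 15.8%. For 1/25 = 4.0%, the exact interval is 0.1–20.4%.

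**5. How often the hospitalization term might matter.** Protocol 1.3.1 and 1.3.2 describe 40 + 60 = 100 earlier patients. Three had a non-arrhythmia admission or prolonged stay: one back pain and two arteriovenous groin fistulae. Back pain is in no CSE category. The fistulae are CSE events only if they required intervention, which the text does not say. So 0 to 3 of 100 would have counted solely through the added term (exact 95% intervals: 1/100, 0.03–5.4%; 3/100, 0.6–8.5%). Suppose the same rate here, inside the window, judged related and coded under that term. The chance of at least one affected subject is then 1 − (1 − p)ⁿ:

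- n = 40: 1 − 0.99⁴⁰ = 33.1%; 1 − 0.97⁴⁰ = 70.4%.
- n = 25: 1 − 0.99²⁵ = 22.2%; 1 − 0.97²⁵ = 53.3%.
- If none qualifies, the chance is zero.

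**6. Windows.** Read literally, 30 ≤ excludes an event 10 days after the procedure, which is the reverse of within 30 days. The sizing in step 5 assumes the intended reading. For late events, 365 − 360 = 5 days are lost before the nominal 12-month visit. The visit window, days 335–395, has 61 days, of which 35 (361–395) lie after day 360. The effect on PV stenosis is probably small, since CT/MRI is scheduled only at baseline and 75 days.

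**7. Related SAEs.** A subject can appear in both the device-related and the procedure-related row, so the single combined proportion cannot be recovered by adding them.

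**The case against.** The practical effect depends on a form nobody outside the study can see. If the committee codes its endpoint field only with Protocol 6.1 events, the added terms never become positive. Seriousness and relatedness may also be settled at adjudication, so re-testing them in SAP 2.5 could be redundant. This stands, but it neutralizes only the additions: thromboembolism would still have no variable.

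The 33–70% figures are soft. The earlier studies give no timing or relatedness for the back-pain admission, and this study introduces a new catheter and extra-PV ablation. An AV fistula is Protocol Table 4's own example of a vascular access complication, so the fistulae might be coded there. That would leave at most 1 of 100 through the added term. This is fair; the figures are conditional, with zero as the lower bound.

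Days 366–395 are visit tolerance and not clearly endpoint time, so the definite late gap is 5 days. Also fair.

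Protocol Note 3 sits inside the adverse-device-effect definition, and the endpoint does not cite it. Applying it is an inference, though its wording covers this protocol and Protocol 7.3.3 uses the same threshold. The wider SAP rule cannot understate harm relative to the narrower one. The choice of alternative procedure-related cut-offs is a preference.

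The SAP was written to protocol Rev C, while the supplied protocol is Rev E. That cannot explain the composite mismatch, because the SAP itself carries the Protocol 6.1 list in 2.4.8.1 and Table 8.

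**Conclusion.** The concern holds and must be fixed. The SAP contradicts its own definition of the primary safety endpoint, and following SAP 2.5 would compute a different composite. The minimum scale is one subject: 2.5 percentage points at N = 40, or 4.0 at N = 25. The net direction is unknown. The conclusion rests on the name mapping stated above. The size of the effect rests on how the adjudication field is coded and on the early windows being read as within 30 and within 7 days. Severity rests on the composite mismatch alone; the related-SAE point is secondary.

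**What to change.** - **Components.** Use only the Protocol 6.1 items in all three rules. Add 30-day and 7-day thromboembolism variables, drop the added terms, and set Total = Early or Late. The overall rule then has 12 terms and each early rule 10.
- **Mappings.** State the name equivalences. Say how requiring intervention is established, and how persistent paralysis is established (Protocol Table 4 explains it under the word permanent, as unresolved at the end of follow-up). State that the adjudication field is completed only for device- or procedure-related SAEs.
- **Windows.** Correct the inequalities to within 30 and within 7 days of an Index or Remap Procedure, with the two windows bracketed together before the event condition. Reconcile day 360 with follow-up through 12 months.
- **Table 12.** Write a rule for the top row and relabel the 30-day sub-row.
- **Extra events.** Report pneumothorax, pulmonary edema and hospitalization descriptively, outside the CSE.
- **Related SAEs.** Define device-related as probable or causal, stating that causal is read as the protocol's definitely, and show the rate including possible beside it. The protocol gives no procedure-related cut-off, so fix one in advance and preferably show alternatives. Add the single combined proportion. As a clarification, state that these rows are per subject over all ITT subjects, with No where there is no qualifying event.

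The cost is SAP wording and programming. If the adjudication form has no thromboembolism value, the committee may need to re-code from existing SAE records. The device-related rate may look lower, which is why the row including possible should sit beside it.

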2.2. Sample size calculation

This investigation is the next phase of ongoing feasibility studies to allow the controlled introduction of a new cardiac ablation catheter (FARAFLEX Endocardial Ablation Catheter). This is a feasibility study with no formal hypothesis testing and therefore no required sample size. Study results will be presented using descriptive statistics. Results from this study will be used to inform and design additional clinical studies.

Forty (40) subjects at up to four sites will allow the assessment of the modified devices and the initial experience and training of investigators and study staff at a new investigational site.

CONFIDENTIEL / CONFIDENTIAL

Toute reproduction ou distribution, totale ou partielle, de ce document, sans autorisation préalable de ICON PLC est interdite.
Reproduction and distribution of this document, in whole or in part, is strictly forbidden without prior authorization from ICON PLC.

	STATISTICAL ANALYSIS PLAN	FARAPULSE PersAFOne SAP V1.0 PERSAFONE Page 14 /49
---	----------------------------------	--

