2.4.8.1. Primary Safety Analysis

The primary safety endpoint for this study is the Composite Safety Endpoint (CSE) defined as the incidence of the following early-onset and late-onset serious adverse events (SAEs) which are device- or procedure-related, as adjudicated by the CEDMC.

CONFIDENTIEL / CONFIDENTIAL

Toute reproduction ou distribution, totale ou partielle, de ce document, sans autorisation préalable de ICON PLC est interdite.
Reproduction and distribution of this document, in whole or in part, is strictly forbidden without prior authorization from ICON PLC.

STATISTICAL ANALYSIS PLAN

FARAPULSE PersAFOne SAP V1.0

PERSAFONE

Page 18 /49

Composite Safety Endpoint Definitions:

Early onset (within 30 days of an Index or Remap Procedure)

- Death
- Myocardial infarction (MI)
- Persistent diaphragmatic paralysis
- Stroke or transient ischemic attack (TIA)
- Peripheral or organ thromboembolism
- Pericarditis
- Cardiac tamponade / perforation
- Vascular access complications requiring intervention
- Heart block

Late onset (any time during follow-up through 12 months):

- Pulmonary vein (PV) stenosis (> 70% diameter reduction from baseline)
- Atrio-esophageal fistula

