2.4.8.2. Secondary Safety Analysis

The proportion of subjects reporting one or more SAEs for each follow-up interval. The intervals will include the period from:

- The Primary Safety Endpoint assessed at 7 rather than 30 days
- The proportion of subjects with a device- or procedure-related SAE
- The proportion of subjects with stroke or TIA
- The proportion of subjects requiring cardioversion
- The proportion of subjects requiring an arrhythmia-related hospitalization.

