COUNT of [(Left Superior Isolated/Blocked ='Yes', Left Inferior Isolated/Blocked='Yes', Left Common Ostium Isolated/Blocked='Yes', Right Middle Isolated/Blocked='Yes', Right Superior Isolated/Blocked='Yes', Right Inferior Isolated/Blocked='Yes')] / COUNT of [(Left Superior Isolated/Blocked in (Yes, No) , Left Inferior Isolated/Blocked in (Yes, No), Left Common Ostium Isolated/Blocked in (Yes, No), Right Middle Isolated/Blocked in (Yes, No), Right Superior Isolated/Blocked in (Yes, No), Right Inferior Isolated/Blocked in (Yes, No))] **in Procedural data form (PR)**
- Derived criteria "Proportion of all ablated pulmonary veins isolated using the study device during the Index Procedure that remain isolated at the 75-day remapping procedure" will be defined as follows:
(Derived criteria "Total number of veins isolated" - Derived criteria "Number of veins with gaps")/ Derived criteria "Total number of veins isolated"
- Derived criteria Proportion "Chronic CTI at 75d remap" will be defined as follows:
IF CTI lesion durable ='Yes' **in Follow-up 3D electroanatomical mapping form (RM)** **THEN** Chronic CTI at 75d remap ='Yes'
ELSE IF CTI lesion durable ='No' **in Follow-up 3D electroanatomical mapping form (RM)** **THEN** Chronic CTI at 75d remap ='No'
- Derived criteria Proportion "LAPW chronic isolation" will be defined as follows:
IF Anatomical Structure/Area other specification 1 **IN** ("POSTERIOR WALL" "LA POSTERIOR WALL" "LAPW" "PA WALL" "BOX POSTERIOR WALL") **AND** Other 1 Lesion durable = 'yes' **OR** Anatomical Structure/Area other specification 2 **IN** ("POSTERIOR WALL" "LA POSTERIOR WALL" "LAPW" "PA WALL" "BOX POSTERIOR WALL") **AND** Other 2 Lesion durable = ='Yes' **in Follow-up 3D electroanatomical mapping form (RM)** **THEN** LAPW chronic isolation= 'Yes'

CONFIDENTIEL / CONFIDENTIAL

Toute reproduction ou distribution, totale ou partielle, de ce document, sans autorisation préalable de ICON PLC est interdite.
Reproduction and distribution of this document, in whole or in part, is strictly forbidden without prior authorization from ICON PLC.

	STATISTICAL ANALYSIS PLAN	FARAPULSE PersAFOne SAP V1.0 PERSAFONE Page 26 /49
---	----------------------------------	--

ELSE LAPW chronic isolation = 'No'

Primary Safety endpoint

Unless otherwise indicated, all the following variables will be derived from the Adverse event adjudication form (CE)

- Derived criteria "Death" will be defined as follows:

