IF (30≤ (EVENT DATE-PROCEDURE DATE IN **PROCEDURAL DATA FORM (PR)**) **OR** (30≤ (EVENT DATE-REMAPPING DATE IN **FOLLOW-UP 3D ELECTROANATOMICAL MAPPING FORM (RM)**) **AND** PRIMARY SAFETY ENDPOINT EVENT CRITERIA=' CVA' **THEN** CVA='Yes'.
ELSE CVA='No'.

- Derived criteria "Major pericarditis" will be defined as follows:
IF (30≤ (EVENT DATE-PROCEDURE DATE IN **PROCEDURAL DATA FORM (PR)**) **OR** (30≤ (EVENT DATE-REMAPPING DATE IN **FOLLOW-UP 3D ELECTROANATOMICAL MAPPING FORM (RM)**) **AND** PRIMARY SAFETY ENDPOINT EVENT CRITERIA=' Major pericarditis' **THEN** Major pericarditis ='Yes'.
ELSE Major pericarditis ='No'.
- Derived criteria "Tamponade/Perforation" will be defined as follows:
IF (30≤ (EVENT DATE-PROCEDURE DATE IN **PROCEDURAL DATA FORM (PR)**) **OR** (30≤ (EVENT DATE-REMAPPING DATE IN **FOLLOW-UP 3D ELECTROANATOMICAL MAPPING FORM (RM)**) **AND** PRIMARY SAFETY ENDPOINT EVENT CRITERIA=' Tamponade/Perforation' **THEN** Tamponade/Perforation ='Yes'
ELSE Tamponade/Perforation ='No'.
- Derived criteria "Pneumothorax" will be defined as follows:
IF (30≤ (EVENT DATE-PROCEDURE DATE IN **PROCEDURAL DATA FORM (PR)**) **OR** (30≤ (EVENT DATE-REMAPPING DATE IN **FOLLOW-UP 3D ELECTROANATOMICAL MAPPING FORM (RM)**) **AND** PRIMARY SAFETY ENDPOINT EVENT CRITERIA=' Pneumothorax' **THEN** Pneumothorax ='Yes'
ELSE Pneumothorax ='No'
- Derived criteria "Heart Block" will be defined as follows:
IF (30≤ (EVENT DATE-PROCEDURE DATE IN **PROCEDURAL DATA FORM (PR)**) **OR** (30≤ (EVENT DATE-REMAPPING DATE IN **FOLLOW-UP 3D ELECTROANATOMICAL MAPPING FORM (RM)**) **AND** PRIMARY SAFETY ENDPOINT EVENT CRITERIA=' Heart Block' **THEN** Heart Block ='Yes'
ELSE Heart Block ='No'
- Derived criteria "Pulmonary Edema" will be defined as follows:
IF (30≤ (EVENT DATE-PROCEDURE DATE IN **PROCEDURAL DATA FORM (PR)**) **OR** (30≤ (EVENT DATE-REMAPPING DATE IN **FOLLOW-UP 3D ELECTROANATOMICAL MAPPING FORM (RM)**) **AND** PRIMARY SAFETY ENDPOINT EVENT CRITERIA=' Pulmonary Edema' **THEN** Pulmonary Edema ='Yes'
ELSE Pulmonary Edema ='No'
- Derived criteria "New or Prolonged Hospitalization, excl. AF/AFL" will be defined as follows:
IF (30≤ (EVENT DATE-PROCEDURE DATE IN **PROCEDURAL DATA FORM (PR)**) **OR** (30≤ (EVENT DATE-REMAPPING DATE IN **FOLLOW-UP 3D ELECTROANATOMICAL MAPPING FORM (RM)**) **AND** PRIMARY SAFETY ENDPOINT EVENT CRITERIA=' New or Prolonged Hospitalization, excl. AF/AFL' **THEN** New or Prolonged Hospitalization, excl. AF/AFL ='Yes'

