- Derived criteria “Stroke after index procedure” will be defined as follows:
IF Event name='STROKE' in **Adverse event form** **AND** Event start date ≥ Procedure date in **Procedural data Form (PR)** **THEN** STROKE='Yes'
ELSE STROKE='No'
- Derived criteria “Transient Ischemic Attack (TIA) after index procedure” will be defined as follows:
IF Event name=' Transient Ischemic Attack' in **Adverse event form** **AND** Event start date ≥ Procedure date in **Procedural data Form (PR)** **THEN** TIA='Yes'
ELSE TIA='No'
- Derived criteria “Stroke after Remap procedure” will be defined as follows:
IF Event name='STROKE' in **Adverse event form** **AND** Event start date ≥ Remap date IN **FOLLOW-UP 3D ELECTROANATOMICAL MAPPING FORM (RM)** **THEN** STROKE='Yes'
ELSE STROKE='No'
- Derived criteria “Transient Ischemic Attack (TIA) after Remap procedure” will be defined as follows:
IF Event name=' Transient Ischemic Attack' in **Adverse event form** **AND** Event start date ≥ Remap date in **FOLLOW-UP 3D ELECTROANATOMICAL MAPPING FORM (RM)** **THEN** TIA='Yes'
ELSE TIA='No'
- Derived criteria “Arrhythmia-related (AF, AFL, AT) hospitalization” will be defined as follows:
IF Arrhythmia-related (AF, AFL, AT) hospitalization ='Yes' in **MDT excel file** **THEN** Arrhythmia-related (AF, AFL, AT) hospitalization ='Yes'
ELSE IF Arrhythmia-related (AF, AFL, AT) hospitalization ='No' in **MDT excel file** **THEN** Arrhythmia-related (AF, AFL, AT) hospitalization ='No'
- Derived criteria “Death” will be defined as follows:
IF SAE: Death='Yes' in **Adverse event form** **OR** Reason ='Patient death' in **study exit form** **THEN** Death='Yes'
ELSE Death='No'

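### SAP 2.5 reuses variable names: the 7-day safety composite reads names that no rule sets, and the Death, stroke and TIA names each carry conflicting rules

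*SAP*

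**What the plan says.** SAP 2.4.8.1 sets the early part of the Composite Safety Endpoint (CSE) as "Early onset (within 30 days of an Index or Remap Procedure", restricted to adjudicated device- or procedure-related serious events. SAP 2.4.8.2 adds a secondary endpoint: "The Primary Safety Endpoint assessed at 7 rather than 30 days".

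SAP 2.5 turns these into IF/THEN/ELSE rules. Three features matter here.

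- **7-day components.** Each of the twelve rules has a heading ending in '7 days', but its THEN and ELSE assign the name without that suffix. Heart block is typical: the 30-day rule assigns "Heart Block ='Yes" and the 7-day rule assigns "Heart Block = 'Yes", which is the same variable. The 7-day composite tests suffixed names such as "Myocardial infarction 7 days='Yes".
- **Death.** The Primary Safety part of SAP 2.5 defines Death from the adjudication form with a date condition. The last rule of the Secondary Safety part has the same heading and the same target. It begins "SAE: Death='Yes' in" the adverse event form, accepts the study exit form as an alternative, and has no date condition.
- **Stroke and TIA.** Near the end of SAP 2.5, STROKE and TIA are set from the adverse event form for events on or after the index procedure. Both are then set again, under the same names, for events on or after remap, with ELSE 'No'.

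The primary composite and its early and late totals come before all the 7-day rules and before the later Death, stroke and TIA rules.

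**The concern.** SAP 2.5 exists so that a programmer can derive the safety endpoints without guessing. Here one name stands for several quantities. Death has to serve the CSE row in Table 8, the 7-day block of Table 12 and all-cause mortality in Table 16. TIA has to serve the adjudicated 30-day component, the 7-day component and two unadjudicated versions from the adverse event form. Table 12 has one Stroke row and one TIA row for the separate stroke/TIA endpoint and does not say which rule fills them.

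At stake are a secondary safety endpoint that may come out empty, component rows in the primary safety table that may disagree with the composite row above them, and stroke/TIA rows that may omit events following the index ablation. The study has "no formal hypothesis testing and therefore no required sample size", so these descriptive counts are the result.

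**Working it through.** The plan has no numerical figure to reproduce on this point. The check traces the rules of SAP 2.5 in the order printed.

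| Step | Rule | Name in heading | Name assigned or read | Date condition |
|---|---|---|---|---|
| 1 | 30-day components | unsuffixed | assigns unsuffixed | 30-day |
| 2 | Primary composite and totals | composite | reads unsuffixed | none of its own |
| 3 | Twelve 7-day components | '7 days' | assigns unsuffixed | 7-day |
| 4 | 7-day composite | composite | reads ten '7 days' names | none of its own |
| 5 | Stroke, TIA after index | distinct | assigns STROKE, TIA | lower bound only |
| 6 | Stroke, TIA after remap | distinct | assigns STROKE, TIA | lower bound only |
| 7 | Second Death | Death | assigns Death | none |

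**7-day composite.** Taking the THEN/ELSE target as the variable, step 3 sets none of the ten names read at step 4. SAP 2.5 opens by making a derived criterion missing when any needed item is missing, so the composite is missing for everyone. If unset is treated only as not 'Yes', the composite's own ELSE gives 'No' for everyone.

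**Stroke and TIA.** Every event on or after remap is also on or after index, so step 6 can only remove events that step 5 counted. The events lost are those from index up to remap. With remap planned at 75 ± 15 days, that is the first 60 (75 − 15) to 90 (75 + 15) days, which contains the whole 30-day window after the index procedure.

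**Single-event test subjects.** Assumptions: remap on day 75, windows as intended (days 0–30 and 0–7), THEN/ELSE target taken as the name, and names not case-sensitive in the SAS software named in SAP 3.

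| Event | Component at step 2 | Component after step 7 |
|---|---|---|
| Tamponade day 1 | Yes | Yes |
| Tamponade day 10 | Yes | No |
| Myocardial infarction day 20 | Yes | No |
| TIA day 3 | Yes | No |
| TIA day 20 | Yes | No |
| TIA day 200 | No | Yes |
| Death day 5 | Yes | Yes |
| Death day 200 | No | Yes |
| PV stenosis day 120 | Yes | Yes |

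The stored component changes for six of nine. The primary composite, evaluated at step 2, changes for none. If it is evaluated after step 7, it changes for the same six.

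**Same subjects, heading taken as the name.** The 7-day composite works: 'Yes' for tamponade day 1, TIA day 3 and death day 5; 'No' for tamponade day 10, myocardial infarction day 20 and TIA day 20. The duplicate Death remains, because its heading and target are both identical. Death on day 200 still overwrites the 30-day component, and it enters the primary composite if that is evaluated last.

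**Independence from the window inequalities.** SAP 2.5 prints the windows as lower bounds (30≤, 7≤), which is a separate defect. With those bounds and THEN/ELSE targets, components change for three of nine subjects (tamponade day 10, myocardial infarction day 20, death day 5), and the 7-day composite is still unset. Correcting the inequalities therefore does not remove the name collision.

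**Weight of one subject.** 1/25 = 4.0 percentage points (N=25 is printed in the shells of Tables 5 and 19); 1/40 = 2.5 points at planned enrolment.

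**The case against.** The strongest defence is that SAP 2.5 is prose pseudo-code and that its headings are the names. The 7-day headings match what the 7-day composite reads, and Tables 8 and 12 call for separate 30-day and 7-day outputs, so the intent can be recovered. Targets are loose elsewhere in the section too: one rule headed for freedom from AF assigns a result labelled AF/AFL/AT. The second Death plainly serves Table 16. A missing composite would also be noticed, unlike a false zero.

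Most of this stands, and it limits the point. A programmer would probably recover the 7-day names. But the headings do not separate the two Death rules, and they do not say which stroke and TIA rule fills the single rows of Table 12.

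A reader might go further and infer that the primary composite, as written, is computed from overwritten values. The documents do not support that: the composite comes before every later rule, and nothing says to derive it last. A reader might also conclude that the 7-day composite must report 0%. The missing-item rule makes an empty result at least as likely. Nor are the later TIA rules free of any date condition: they have a lower bound and lack an upper one. Finally, no percentage bias can be put on the primary composite. The documents do not say what share of early events falls in the first week, or how often late deaths or TIAs are expected.

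**Conclusion.** The rules are wrong as written for reported safety endpoints and should be corrected before programming. This is not a demonstrated error in the primary composite.

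- **7-day composite:** missing or 'No' for every subject if THEN/ELSE targets are followed; correct in this respect if headings are used.
- **Table 8 component rows:** can disagree with the composite row if one dataset variable is reused. The six-of-nine count shows the mechanism in constructed cases and is not an expected rate.
- **Table 12 stroke and TIA rows:** can lose every event between index and remap, and the governing rule is unstated under either reading.
- **Death:** ambiguous under either reading.
- **Primary composite:** exposed only if coded after the later rules.

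**What to change.** In SAP 2.5:

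1. Assign each 7-day result to its own variable (Death_7d, MI_7d, TIA_7d and so on), and have the 7-day composite read those.
2. Rename the later criteria AllCauseDeath (for Table 16), Stroke_postIndex, Stroke_postRemap, TIA_postIndex and TIA_postRemap.
3. State that the stroke and TIA rows of Table 12 for the separate stroke/TIA endpoint use the post-index variables.
4. State that the CSE and its Table 8 rows use only the adjudicated components in the Primary Safety part of SAP 2.5. This includes the component named CVA for the row labelled Stroke, since the only variable called STROKE is the unadjudicated one.

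The cost is SAP wording and program variable names. No new data, visits or adjudication are needed. The window inequalities need their own correction.
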